#### **3.5.1.2 Statistical Methods for Safety Analyses**

There are no safety topics of special interest in this study.

Table 1 Analysis Strategy for Safety Parameters

Analysis Part	Safety Endpoint	Descriptive Statistics	95% Between-group CI
Overall Safety Assessment	Any AE	X	X
	Any serious AE	X	X
	Any drug-related AE	X	X
	Any Grade 3 to 4 AE	X	X
	Any serious and drug-related AE	X	X
	Any Grade 3 to 4 and drug-related AE	X	X
	Discontinued study intervention due to AE	X	X
	AE that resulted in death	X	X
	Specific AEs, SOCs, or PDLCs	X	
	Change from baseline results for laboratory values	X	

AE=adverse event; CI=Confidence Interval; PDLC=Pre-Defined Limit of Change; SOC=System Organ Class.

### **Handling of Missing Data in Safety Analyses**

Missing safety parameters, unless otherwise specified, will not be imputed; as such, any participant with a missing value will be excluded from the analysis. Change from baseline summaries require a baseline value. Baseline measurements are defined as the Day 1 value for each participant. In the rare event when data for this visit are missing, the value obtained at the most recent screening visit prior to Day 1 will be used as baseline, when available. If no baseline result is available for a given analysis, that participant will not be included in the analysis.

### **3.5.2 Statistical Methods for Pharmacokinetic Analyses**

Plasma MK-8527 endpoints will be summarized separately by dose level as appropriate, with geometric means and %GCV.

### **3.5.3 Demographic and Baseline Characteristics**

The comparability of the treatment groups for each relevant demographic and baseline characteristic will be assessed using tables. No statistical hypothesis tests will be performed on these characteristics. The number and percentage of participants screened and randomized and the primary reasons for screening failure and discontinuation will be displayed. Demographic variables (eg, age), baseline characteristics, primary and secondary diagnoses, and prior and concomitant therapies will be summarized by treatment group either by descriptive statistics or categorical tables.

### **3.5.4 Population PK Analyses**

Based on PK data obtained within this study, a separate population PK analysis will be performed. The prospective details of this analysis will be specified in a separate population PK analysis plan.

### **3.6 Interim Analyses**

The siDMC will be responsible for an interim safety review. An interim safety analysis will be performed once 50% of the planned enrollment has reached Week 12 or discontinued from study intervention.

Treatment-level results and/or participant-level data from the IA will be provided by the unblinded statistician to the siDMC which consists of Sponsor personnel. Limited additional Sponsor personnel may be unblinded to the treatment-level results of the IAs, if required, to act on the recommendations of the siDMC. The list of individuals who are unblinded with respect to results of IAs will be documented by the unblinded statistician.

The processes by which recommendations and decisions are reached and communicated are documented in the siDMC charter. Individuals who have been unblinded at any level will not be involved in any discussions regarding modifications to the protocol, statistical methods, identification of protocol deviations, or data validation efforts after the IA.

An intervention group may be recommended for early termination due to safety concerns based on the following criteria along with an evaluation of the totality of safety data.

- At least 10% of participants meet discontinuation criteria as detailed in Table 3 of Section 7.1 of the protocol.
- The upper bound of the 95% CI of the difference between the treatment group and the placebo group for the percent change from baseline in lymphocyte count is less than 0.

If at least 10% of participants in a study intervention group meet discontinuation criteria as detailed in Table 3 of Section 7.1 of the protocol, study enrollment will be paused until the siDMC review has been completed.

In addition to the planned IA review, an ad hoc siDMC review will be triggered if  $\geq 10\%$  of all enrolled participants meet the criteria as detailed in Table 3 of Section 7.1 of the protocol at any point during the course of the study. During this time, enrollment in the study will be paused until the siDMC review has been completed.

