4 STUDY DESIGN

4.1 Overall Design

This is a randomized, double-blind, placebo-controlled, parallel-group, multicenter study of oral MK-8527 administered QM in adults who are at low-risk of HIV-1 infection.

Approximately 350 participants will be randomized in a 2:2:2:1 ratio to 1 of 4 intervention groups: Group 1: MK-8527 (3 mg); Group 2: MK-8527 (6 mg); Group 3: MK-8527 (12 mg); and Group 4: Placebo. The screening window is 45 days and participants are allowed to rescreen 1 time (Section 8.11.1.2). The study population composition targets are: $\geq 30\%$ women, $\geq 30\%$ men, $\geq 80\%$ aged ≤ 35 years, and $\geq 30\%$ enrolled in Africa. Randomization will be stratified by sex (female, male) and region (Africa, non-Africa).

Participants will receive a total of 6 oral doses of the assigned blinded study intervention, 1 dose every 4 weeks, starting on Day 1. The final dose will be administered at the Week 20 visit. After the last dose, all participants will complete an 8-week blinded follow-up period.

The primary safety assessment will include all accumulated safety data during the intervention and follow-up period. AEs leading to discontinuation from study intervention will be assessed until Week 20 (last dose received). The Sponsor will perform an ongoing comprehensive review of safety parameters to assess for overall trends and outliers in reported AEs and event toxicities per standard monitoring procedures.

All participants will be evaluated for plasma MK-8527 PK drug levels, and a subset (approximately N=20 participants per intervention group) will be evaluated for MK-8527-TP in PBMC (PBMC Subset).

All participants and the investigators/clinical site personnel directly associated with study conduct will remain blinded to study intervention assignment through the 8-week follow-up period. The siDMC (internal) will be responsible for an interim safety review once 50% of the planned enrollment has reached Week 12 or discontinued from study intervention. Additional meetings of the siDMC may be triggered based on criteria outlined in the SAP/siDMC charter. An unblinded Sponsor team will review PK and safety data on an ongoing basis for the duration of the study. As per amendment 02, all Sponsor personnel except for a blinded medical monitoring team will be unblinded after the last expected Follow-up Week 4 visit, to enable earlier program strategic decision-making by the Sponsor.

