4.2.1.1 Safety Endpoints

The primary safety endpoints are the number of participants experiencing AEs and the number of participants discontinuing study intervention due to AEs. Safety evaluations will include physical examinations (including vital signs) and laboratory tests performed per the SoA (Section 1.3). AEs will be evaluated at each visit and assessed according to the guidelines in Section 8.4. Participants may be asked to return for unscheduled visits in order to perform additional safety monitoring.

Dose-dependent decreases in total lymphocyte and lymphocyte subset counts were observed in clinical studies with ISL, another investigational NRTI agent. The risk of lymphocyte decreases for MK-8527 at the proposed doses is considered low based on available nonclinical and clinical data. To further assess the risk, hematology with lymphocyte subset counts will be monitored, in conjunction with MK-8527 in plasma and MK-8527-TP in PBMC measurements to allow correlation with any dose-related effects.

In this study, criteria for discontinuation of study intervention for confirmed on-treatment decreases of total lymphocyte count <1000 cells/mm 3 or CD4+ T-cell count <500 cells/mm 3 are based on literature that identifies an increased frequency of infections or increased risk of infections when cell counts drop below these levels, whether caused by disease (eg, HIV infection, systemic lupus erythematosus, rheumatoid arthritis) or by disease-modifying drugs [Giovannoni, G., et al 2018] [Spiezia, A. L., et al 2022] [Merayo-Chalico, J., et al 2013] [Subesinghe, S., et al 2020] [Warny, M., et al 2018], and DAIDS criteria (Version 2.1, July 2017) [National Institute of Allergy and Infectious Diseases 2017]. In addition, discontinuation requires a confirmed $\geq 30\%$ decrease from baseline in either total lymphocytes or CD4+ T-cell counts (Table 3) so that participants whose baseline total lymphocyte counts or CD4+ T-cell counts are just above the discontinuation thresholds are

not discontinued for laboratory findings that are within the natural variability of these tests. A $\geq 30\%$ decrease was chosen based on published literature demonstrating that lymphocyte counts vary as much as 25% in healthy adults when measured as frequently as day-to-day and over longer periods of time (every 6 months for many years) [Aziz, N., et al 2019] [Aziz, N., et al 2019a] [Statland, B. E., et al 1978].

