6.3.2 Stratification

Intervention randomization will be stratified according to the following factors:

1. Sex (female, male) (as assigned at birth)
2. Region (Africa, non-Africa)

The effects of study interventions may differ between these subgroups of sex and region. Therefore, sex and region are selected as the stratification factors to ensure that intervention groups will be well-balanced, and the effects of study interventions will not be confounded by those demographic characteristics.

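### The interim lymphocyte criterion in SAP 3.6 names no visit, model or covariates and no link between its two bullets; one named visit and an adjusted CI would sharpen it at almost no cost

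*SAP*

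**What the plan says.** **The criterion.** SAP 3.6 says a group may be recommended for early termination "based on the following criteria along with an evaluation of the totality of safety data". The first bullet is that at least 10% of participants meet the lymphocyte or CD4+ discontinuation criteria in Protocol Table 3. The second, for lymphocyte count, is met when "The upper bound of the 95% CI of the difference between the treatment group and the placebo group for the percent change from baseline" falls below 0. No visit, summary over visits, estimator or covariate is given, and nothing says whether one bullet suffices or both are needed.

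**Timing and size.** "An interim safety analysis will be performed once 50% of the planned enrollment has reached Week 12 or discontinued from study intervention" (SAP 3.6). Protocol 4.1 gives the allocation: "Approximately 350 participants will be randomized in a 2:2:2:1 ratio to 1 of 4 intervention groups".

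**Baseline.** "Baseline measurements are defined as the Day 1 value for each participant" (SAP, Handling of Missing Data in Safety Analyses). The latest screening value is used only if Day 1 is missing.

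**Method.** SAP Table 1 gives laboratory change from baseline descriptive statistics only, with no between-group CI. SAP 3.8.1 bases Table 2 on a two-sample t-test at 100 vs 50. SAP 3.7 plans no multiplicity adjustment.

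**Data in hand.** The Schedule of Activities has hematology at Screening and at Day 1. Protocol 6.3.2 says "sex and region are selected as the stratification factors to ensure that intervention groups will be well-balanced".

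**The concern.** Protocol 2.3 and 4.2.1.1 single out lymphocyte decline as the risk seen with another drug in the class. This criterion is the one place where the SAP plans a between-group interval on it. Two separate things are at stake.

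*Precision.* Percent change divides by a single Day 1 count, and Protocol 4.2.1.1 accepts that "lymphocyte counts vary as much as 25% in healthy adults". That noise passes straight into the estimate. A second pre-treatment count and both stratification factors are available to remove some of it, but the SAP does not say they will be used. The loss matters most at the interim, where the groups are half the size assumed in Table 2.

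*Definition.* By the interim, every participant who has reached Week 12 should have counts at Day 2 and Weeks 4, 8 and 12. Without a named visit, the chance of meeting the criterion by luck depends on which reading is used. The choice could be made by Sponsor personnel who have already seen unblinded data.

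**Working it through.** **1. Reproduce the SAP's figure.** Inputs from SAP 3.8.1: SD 20, difference 10, 100 vs 50, two-sided 5%. The noncentral-t power of a two-sample t-test is 81.8%, as stated. The half-width at that size is 6.85 points. Table 2 is not in error; it describes the full sample.

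**2. Move to the interim size.** 50% of 350 is 175. Split 2:2:2:1, that is about 50 per dose and 25 on placebo.
- Half-width = t(0.975, 73) × 20 × √(1/50 + 1/25) = 1.993 × 20 × 0.245 = 9.8 points.
- Chance that the upper bound is below 0 at a true -10% difference: 52.2%.

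**3. Add baseline adjustment.** Let ρ be the correlation between two counts in the same person. The documents give no ρ, so a range is shown.
- Day 1 only: adjusted SD / change-score SD = √((1+ρ)/2).
- Day 1 plus screening, if screening predicts as well as Day 1: ratio = √{[1 − 2ρ²/(1+ρ)] / [2(1−ρ)]}.

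| ρ (assumed) | Day 1: SD ratio | Half-width | Flagged at -10% | Day 1 + screening: SD ratio | Half-width | Flagged at -10% |
|---|---|---|---|---|---|---|
| 0.5 | 0.866 | 8.5 | 64% | 0.816 | 8.0 | 69% |
| 0.7 | 0.922 | 9.0 | 59% | 0.840 | 8.2 | 67% |
| 0.8 | 0.949 | 9.3 | 56% | 0.850 | 8.3 | 66% |
| 0.9 | 0.975 | 9.5 | 54% | 0.858 | 8.4 | 65% |

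The CI is therefore about 3-13% narrower with Day 1 alone and 14-18% narrower with both counts. The table holds the percent-change SD at 20 while ρ varies. As a check with one coherent set of assumptions, log-normal counts with between-person CV 25% and within-person CV 15% imply ρ = 0.73 and a percent-change SD of about 22. Day 1 adjustment then narrows the simulated half-width from 10.60 to 9.95 with no effect (about 6%), and raises flagging at -10% from 52% to 58%.

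**4. Chance findings with no drug effect.** A two-sided 95% CI acted on in one direction gives a nominal 2.5% per dose. Three independent comparisons would give 1 − 0.975³ = 7.3%; sharing one placebo group lowers this to about 5.6%. Simulation at 25/50/50/50 with log-normal counts and several assumed variabilities:

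| Reading of the criterion | At least one of three doses flagged |
|---|---|
| One fixed visit, the average or the nadir | about 6% |
| One fixed visit, Day 1-adjusted | about 6% |
| Any of Weeks 4, 8, 12 | 14-16% |
| Any of Day 2, Weeks 4, 8, 12 | 17-19% |

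Adjustment leaves the rate unchanged. The number of visits allowed to count is what moves it.

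**The case against.** Several points against this stand.

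- *The SAP is silent, not prescriptive.* A reader might infer that it requires an unadjusted comparison. It does not: the t-test appears only in the power section, and Protocol 9.6 defers further interim details to the SAP and the siDMC charter, which is not among the documents. Still, SAP 3.6 assigns the charter the process for recommendations and states the criterion itself, so the statistic should be defined there.
- *The criterion does not stop a group.* It is weighed with all the safety data, and Protocol 10.1.4.1 has the Executive Oversight Committee decide on recommendations. The percentages above describe one input to a committee.
- *Other safeguards exist.* These are the individual discontinuation criteria in Protocol Table 3, the 10% criterion with its enrollment pause, the ad hoc siDMC trigger, the lymphocyte and CD4+ events of clinical interest, and ongoing unblinded review. It would be too strong to say that a real fall would go unnoticed.
- *The 52% is mainly a matter of size.* Even full adjustment reaches only 65-69%, and that needs a screening count, up to 45 days older, to predict as well as Day 1. Screening counts are also cut off at 1000 cells/mm³ by eligibility and may be repeated once.
- *Regression to the mean is not a bias here.* In a randomized comparison it costs precision, and the CI already reflects that.
- *Nothing says any visit suffices.* The SAP refers to a single difference. The inflation is a risk left open by the wording, not a property of it.

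**Conclusion.** The criterion is under-specified, and a better-defined version is available from data already planned. An unadjusted CI at about 50 vs 25 and SD 20 has half-width 9.8 points and 52% sensitivity at -10%. Day 1 adjustment gives a modest gain (54-64%), and adding screening gives up to 65-69%. Both ranges rest on an assumed ρ of 0.9 to 0.5, and the second also on screening predicting as well as Day 1. The gain from sex and region cannot be quantified from the documents.

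The visit gap is a separate fault. It can move the no-effect chance of flagging some dose from about 6% to 14-16% or 17-19%, but only if any visit may count. A reader might attribute that inflation to the lack of adjustment; the rates in step 4 rule this out. Requiring both bullets would lower the rate, but the SAP does not say how they combine. The 50 vs 25 split is the expected one. Enrollment may still be open at the interim, which could add early-visit data.

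**What to change.** In SAP 3.6, and in the siDMC charter to match:

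1. State that the CI comes from an ANCOVA at one named visit, for example Week 12, or the last value up to Week 12 for those who stopped early, which matches the interim trigger.
2. Adjust for the Day 1 and screening lymphocyte counts, sex and region. Log counts back-transformed to a percent difference are one option; the small downside is that the estimate becomes a geometric-mean ratio rather than Table 2's mean percent change.
3. Keep the existing threshold of an upper bound below 0.
4. Have the sponsor state how the two bullets combine.
5. Report the criterion's operating characteristics at the interim size beside Table 2.

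The cost is wording in two documents and a few lines of code. No new data or participants are needed.

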### **3.7 Multiplicity**

No multiplicity adjustment is planned for this study.

### 3.8 Sample Size and Power Calculations

The sample size of this study will allow for the accumulation of approximately 150 person-years of safety data on MK-8527.

#### 3.8.1 Sample Size and Power for Safety Analyses

**Table 2** summarizes the power under various assumptions of the underlying standard deviation to detect the difference in the mean percent change from baseline in lymphocytes. The power is based on the two-sample t-test assuming 100 participants in the MK-8527 group and 50 in the placebo group. For example, if the standard deviation of percent change from baseline in both groups is 20, this study has 81.8% power to detect a difference at least as large as 10%.

Table 2 Power (%) to Rule Out Difference in Mean Percent Change from Baseline  
(With 100 Participants Randomized to MK-8527 and 50 Randomized to Placebo)

Underlying Standard Deviation of Percent Change from Baseline a	Underlying Difference of Mean Percent Change from Baseline in Lymphocytes (MK-8527 - Placebo)					
	-5%	-10%	-15%	-20%	-25%	-30%
10	81.8	>99.9	>99.9	>99.9	>99.9	>99.9
15	48.1	96.9	>99.9	>99.9	>99.9	>99.9
20	29.9	81.8	99.0	>99.9	>99.9	>99.9
25	20.8	63.1	93.1	99.6	>99.9	>99.9
30	15.8	48.1	81.8	96.9	99.8	>99.9

**Table 3** summarizes the differences in the incidence of AEs (MK-8527 minus placebo) that can be ruled out with different power levels and 95% confidence when there are 100 participants in the MK-8527 group and 50 participants in the placebo group. The underlying incidence of AE is assumed to be the same in the MK-8527 group as that in the placebo group. The calculations are based on an asymptotic method proposed by M&N method [Miettinen, O. and Nurminen, M. 1985]. No multiplicity adjustments were made.

Table 3 Difference in Incidence of AEs (MK-8527 Group Minus Placebo) That Can Be Ruled Out With 100 Participants in the MK-8527 Group and 50 Participants in the Placebo Group

Target Power	Difference a in Percentage Points That Can Be Ruled Out with Target Power Assuming the Underlying Incidence of the AE is				
	10%	20%	30%	40%	50%
80	20	23	24	24	23
85	21	24	25	26	25
90	23	26	27	28	27

aThe upper bound of the two-sided 95% confidence interval M&N method [Miettinen, O. and Nurminen, M. 1985] for the difference in AE incidences assuming the incidences are the same.

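### SAP Table 3 is labelled as AE differences the trial can rule out, but its values are differences it can detect (20 points printed against about 14 at 10% incidence and 80% power)

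*SAP*

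**What the plan says.** SAP section 3.8.1 defines the Table 3 entries in three places, and the three agree.

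- The text describes differences "that can be ruled out with different power levels and 95% confidence" and sets the group sizes at 100 on MK-8527 and 50 on placebo. It adds that "The underlying incidence of AE is assumed to be the same in the MK-8527 group as that in the placebo group" and that "The calculations are based on an asymptotic method proposed by M&N method".
- The title reads "Difference in Incidence of AEs (MK-8527 Group Minus Placebo) That Can Be Ruled Out With 100 Participants in the MK-8527 Group and 50 Participants", followed by the placebo group.
- Footnote a names as the criterion "The upper bound of the two-sided 95% confidence interval M&N method". The footnote specifies that this bound is "for the difference in AE incidences assuming the incidences are the same".

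The printed entries, in percentage points, are:

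| Target power | 10% | 20% | 30% | 40% | 50% |
|---|---|---|---|---|---|
| 80% | 20 | 23 | 24 | 24 | 23 |
| 85% | 21 | 24 | 25 | 26 | 25 |
| 90% | 23 | 26 | 27 | 28 | 27 |

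**The concern.** Ruling out and detecting are different claims. A rule-out figure takes the true difference as zero and asks how large an excess the upper confidence limit will fall below. A detection figure takes the true difference as d and asks how often the lower limit will exceed zero. The label, the assumption and the footnote all describe the first; the numbers look like the second.

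One sign is visible without software. With equal incidence p in both arms, the variance of the observed difference is proportional to p(1-p), which rises up to 50%. The excludable difference should therefore keep rising to 50%. In all three printed rows it falls between 40% and 50%: 24 to 23, 26 to 25, and 28 to 27. Detection from a placebo rate p behaves that way, because the MK-8527 rate p + d moves past 50%.

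AE incidence is the primary endpoint and no hypothesis is tested, so Table 3 is the only planning statement of precision for AE incidence. A reader uses it to judge how large an AE excess this trial could exclude.

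**Working it through.** **Inputs (all from SAP 3.8.1).** MK-8527 n = 100, placebo n = 50, no allowance for dropout; two-sided 95%, so z = 1.96; M&N method, whose variance carries the factor N/(N-1) = 150/149; incidence p of 10 to 50%; power 80, 85 and 90%.

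**1. The calculation that returns the printed figures (detection).** Placebo has incidence p and MK-8527 has p + d. Solve for d:

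power = Φ((d − 1.96·s0)/s1), with s0² = p̄(1−p̄)(1/100 + 1/50)(150/149), p̄ the pooled rate, and s1² = p(1−p)/50 + (p+d)(1−p−d)/100.

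Example at p = 10%, d = 0.196:
- p̄ = (50×0.10 + 100×0.296)/150 = 0.2307
- s0 = √(0.2307×0.7693×0.03×150/149) = 0.0732
- s1 = √(0.10×0.90/50 + 0.296×0.704/100) = 0.0623
- power = Φ((0.196 − 1.96×0.0732)/0.0623) = Φ(0.84) = 80%

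| Power | 10% | 20% | 30% | 40% | 50% |
|---|---|---|---|---|---|
| 80% | 19.592 | 22.575 | 23.855 | 24.001 | 23.216 |
| 85% | 21.062 | 24.162 | 25.464 | 25.568 | 24.685 |
| 90% | 22.917 | 26.147 | 27.467 | 27.509 | 26.499 |

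Fourteen of these round to the printed cell. The last, 26.499 against a printed 27, misses the rounding boundary by 0.001.

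**2. The calculation the SAP describes (rule-out).** Both arms have incidence p. Find the smallest d for which the upper M&N limit falls below d with the target power:

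power = Φ((d − 1.96·s0)/s1), now with s1² = p(1−p)(1/100 + 1/50) and s0² = [p̃1(1−p̃1)/100 + p̃2(1−p̃2)/50](150/149), where p̃1 and p̃2 are the maximum likelihood rates constrained to differ by d.

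Example at p = 10%, d = 0.141:
- p̃1 = 0.1886, p̃2 = 0.0476, so s0 = 0.0495
- s1 = √(0.10×0.90×0.03) = 0.0520
- power = Φ((0.141 − 1.96×0.0495)/0.0520) = Φ(0.85) = 80%

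At the printed d = 0.20, the constrained rates are 0.2404 and 0.0404 and s0 = 0.0512, so power = Φ((0.20 − 1.96×0.0512)/0.0520) = Φ(1.92) = 97%, not 80%.

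| Power | 10% | 20% | 30% | 40% | 50% |
|---|---|---|---|---|---|
| 80% | 14.1 | 18.3 | 21.1 | 22.8 | 23.7 |
| 85% | 15.1 | 19.6 | 22.6 | 24.4 | 25.3 |
| 90% | 16.5 | 21.3 | 24.4 | 26.3 | 27.3 |

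Every row rises through 50%, as it should.

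**3. Exact check.** Enumerating all binomial outcomes and applying the M&N criterion to each gives 13.6, 18.2, 21.0, 22.8 and 23.6 for the 80% row. Exact rule-out power (%) at the printed values is:

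| Printed row | 10% | 20% | 30% | 40% | 50% |
|---|---|---|---|---|---|
| 80% | 98.5 | 94.7 | 89.4 | 84.0 | 77.5 |
| 85% | 99.1 | 96.2 | 91.8 | 89.4 | 83.9 |
| 90% | 99.7 | 98.3 | 95.4 | 93.4 | 89.1 |

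**4. Other readings of rule-out.** Wald limits, a one-sided 5% limit, arms swapped, 50 per arm, a continuity correction, a 1% level, and the upper limit at equal observed rates give between 9.6 and 18.7 at 10% incidence and 80% power. None reaches 20 there, and none fits across the row.

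**The case against.** The strongest objection concerns consequence, not arithmetic. No hypothesis is tested. SAP section 3.8 justifies the sample size by about 150 person-years of exposure, and Protocol section 9.8 does not carry the table. The interim criteria in SAP section 3.6 use the lymphocyte and CD4+ discontinuation criteria and a lymphocyte interval, not this table. At analysis the observed M&N intervals will replace any planning figure. The error is also conservative in 12 of 15 cells: the printed difference can be excluded with at least the stated power. Only the three cells at 50% incidence fall short, by 2.5, 1.1 and 0.9 points of power. The 6-point gap at 10% incidence is the largest in the 80% row; at 40 and 50% the gap is about 1 point.

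All of that stands, and it limits the consequence. It does not make the table right: label, assumption and footnote agree with each other and disagree with the numbers, and nothing elsewhere in the SAP or protocol corrects them.

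A second caution also stands. The SAP names no formula or software beyond M&N, so the detection calculation is an inference about where the numbers came from. With 14 cells matched and the fifteenth at a rounding boundary, it is a strong one. The finding that the printed values are not rule-out values does not depend on it.

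**Conclusion.** Table 3 is wrong as written. Under the SAP's own assumptions (equal true incidence, 100 and 50 participants with no loss, upper limit of the two-sided 95% M&N interval), the printed 80% row exceeds the rule-out difference by about 6, 5, 3 and 1 points at 10, 20, 30 and 40% incidence, and is about 1 point too small at 50%. The printed values are almost certainly detectable differences, which assume that the arms differ by the tabulated amount, the opposite of the stated assumption. The effect is a misstated planning precision for the primary endpoint, mostly in the pessimistic direction.

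**What to change.** Take one of two routes.

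- **Keep the rule-out wording and replace the values.** The smallest whole points that reach the target by exact M&N enumeration are below. This route suits a trial that estimates and does not test.

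| Power | 10% | 20% | 30% | 40% | 50% |
|---|---|---|---|---|---|
| 80% | 14 | 19 | 21 | 23 | 24 |
| 85% | 15 | 20 | 23 | 25 | 26 |
| 90% | 16 | 21 | 25 | 27 | 28 |

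- **Keep the values and relabel.** Call them detectable differences in the title and text, head the columns as placebo incidence, state that MK-8527 has that incidence plus the difference, and delete the equal-incidence sentence and footnote a. Recheck the cell at 90% power and 50% incidence.

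On either route, state the formula or software used. Align the title of Table 2 at the same time: it speaks of ruling out while its text speaks of detecting, and the cells checked there (differences of 5 to 15%) reproduce as two-sample t-test detection power.

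The cost is an edit to one SAP section. Sample size, data collection, interim criteria and planned analyses do not change.
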